9.4.6 SDMT

The change from baseline for the SDMT total score will be summarized based on the mITT analysis set using an MMRM.

The above analysis of change from baseline will be repeated for the subset of subjects with an SDMT total score < 50 at baseline using the same MMRM as described in the previous paragraph. The posterior probability of the difference of the group means being

greater than 1 based on the SDMT total score will be presented. A non-informative prior will be used.

The number and percentage of subjects with a change from baseline in the SDMT total score \geq 4 will be analyzed as observed. The analysis will be presented at each time point with the number and percentage of subjects, difference from placebo in responder rate, and the 95% confidence interval for the difference in proportion of subjects based on Wald confidence limits, and the odds ratio and corresponding 95% confidence interval based on the logistic regression model including baseline as a covariate and treatment as a main effect.

9.4.7 MFIS-5

The change from baseline for the MFIS-5 total score will be summarized based on the mITT analysis set using an MMRM.

The above analysis of change from baseline will be repeated for the subset of subjects with an MFIS-5 total score of \geq 9 at baseline using the same MMRM as described in the previous paragraph. The posterior probability of the difference of the group means being greater than 1 based on the MFIS-5 total score will be presented. A non-informative prior will be used.

9.4.8 Low Contrast Visual Acuity

The change from baseline in low contrast visual acuity variables will be summarized as observed at each time point for the following parameters:

- Number of characters read, bilateral, 100% contrast level
- Number of characters read, bilateral, 2.5% contrast level
- Number of characters read, bilateral, 1.25% contrast level
- Number of characters read, right eye, 100% contrast level
- Number of characters read, right eye, 2.5% contrast level
- Number of characters read, right eye, 1.25% contrast level ۲

- Number of characters read, left eye, 100% contrast level
- Number of characters read, left eye, 2.5% contrast level
- Number of characters read, left eye, 1.25% contrast level

The number of observations, mean, standard deviation, median, min and max will be presented.

The change from baseline in the number of characters read, bilateral at the 1.25% contrast level, will be summarized using an MMRM based on the population of subjects with a baseline deficit, defined as ≤ 11 characters (bilateral at the 1.25% contrast level) at baseline. The posterior probability that the mean difference between groups is > 2 using a non-informative prior will be calculated.

9.4.9 Actigraphy

Actigraphy was collected for 7 days starting at the visits at Week 0 (Baseline), 24, 36, and 52. The actigraphy parameters of movement including average gait cadence, moving duration, walking duration, number of steps and resting duration will be analyzed.

Moving duration, walking duration, number of steps, and resting duration will be normalized for the number of hours per day the subject is wearing the device, i.e., divided by the (device wear time duration [in seconds] \div 3600).

The analysis of change from Week 0 for each of the moving duration, walking duration, number of steps, and resting duration will be based on the average hourly value for that visit, i.e., the Week X value will be the sum of the daily average hourly values for that parameter divided by the number of days the subject wore a sensor within a window. The analysis of change from Week 0 for average gait cadence will be based on the average daily value of gait cadence for that visit, i.e., the Week X value will be the sum of the daily mean gait cadence values divided by the number of days the subject wore a sensor within a window. The pooled standard deviation, effect size, and 95% confidence interval of the effect size will also be noted.

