3.7 Exploratory Endpoints

- 1. Disability improvement response rate on the T25FW, 9HPT, either hand, and EDSS at Weeks 12, 24, 36, and 52, and the EDSS + at Weeks 12, 24, and 36.
- 2. Change from Baseline on the T25FW and 9HPT, either hand, at Weeks 12, 24, 36, and 52
- 3. Disability progression response rate on the EDSS + (T25FW, 9HPT, either hand, EDSS) and for each EDSS + component
- 4. 12- and 24-week confirmed disability improvement response rate on the EDSS + (T25FW, 9HPT, either hand, EDSS) and for each EDSS + component
- 5. Change from Baseline on the MS Impact Scale (MSIS-29) version 2 at Weeks 12, 24, 36, and 52
- 6. Change from Baseline on the Modified Fatigue Impact Scale (MFIS) at Weeks 12, 24, 36, and 52
- 7. Change from Baseline on cognition battery at Weeks 12, 24, 36, and 52:
 - Symbol Digit Modalities Test (SDMT) Oral Version
 - Brief Assessment of Cognition Verbal Memory Immediate Recall BAC App Version

- Brief Assessment of Cognition Tower of London BAC App Version
- Change from Baseline on the Low Contrast Visual Acuity (LCVA) assessments at Weeks 12, 24, 36, and 52
- 9. Change from Baseline in plasma biomarkers at Weeks 12, 24, 36, and 52
- 10. Change from Baseline on the MS Individualized Outcome Assessment (Multiple Sclerosis Individualized Outcome Assessment [MSIOA]) scale at Weeks 24 and 52
- 11. Change from Baseline in one week average daily step count and other activity measures (via home actigraphy with wearable biosensor) initiated at Weeks 24, 36, and 52

MRI Endpoints

The following imaging tests will be conducted. Details will be provided in the Statistical Analysis Plan (SAP).

- Lesion counts and volumes
- Brain and spinal cord atrophy measures
- Magnetization transfer ratio (MTR)
- Diffusion tensor imaging (DTI)

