4 INVESTIGATIONAL PLAN

4.1 Overall Study Design and Plan

This is a 52-week, Phase 2a, proof-of concept, randomized, double-blinded, parallel-group, placebo-controlled multicenter study to evaluate the safety and efficacy of 2 doses of elezanumab in adult subjects with progressive forms of MS who have established disability.

This study will include an approximate 30-day Screening period. The Treatment Period will include 14 visits from Baseline (Week 0) every 4 weeks through Week 52. Doses will be administered via Intravenous (IV) infusion at Week 0 (Baseline) and every 4 weeks thereafter through Week 48 for a total of 13 doses. The follow-up period includes 6 follow-up telephone calls that will occur at Weeks 56 through 76. All visits during the Treatment Period and Follow-up Period will be allowed a window of ± 7 days. Safety parameters such as clinical laboratory test results, ECG, and vital signs will be monitored (see Operations Manual [Appendix F]). Throughout the study and for a period of 39 weeks (5 half-lives) after the time of last study drug administration, females of childbearing potential will undergo monthly pregnancy testing; and for all subjects' AEs will be collected, whether solicited or spontaneously reported by the subject.

Eligible subjects will be randomized at the Week 0 - Baseline Visit to receive either elezanumab or as an IV infusion or placebo in a 1:1:1 ratio (Section 5.8 and Section 7.3). Blinded doses will be administered intravenously every 4 weeks for 48 weeks. Subjects should remain on their current MS treatment regimen throughout the study.

During the Week 0 visit, subjects will be trained on the use of a wearable device. Subjects will be required to use the wearable device for 7 consecutive days at four time points (i.e., starting at the Week 0 visit and after visits at Weeks 24, 36, and 52), in countries where such devices are allowed.

Subjects who discontinue should complete the procedures outlined for the Early Discontinuation (ED) visit as soon as possible, preferably within 2 weeks (Section 5.5 and Section 5.6).

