| Serum pregnancy ter females of childbear | | × | | | | | | | | | | | | | | | | | | | | | | | |

| | SCREENING | | | | | | TF | REATM | ENT | | | | | | | ation | FOL | LOW-U | IP VIRT | UAL TE | LEPHO | NE VISITS |
|---|--|----------------------|--------|--------|---------|---------|---------|---------|---------|---------|---------|---------|---------|---------|---------|-----------------------|---------|---------|---------|---------|---------|---------------------------|
| Activity | 30 days | Week 0 - Baseline | Week 4 | Week 8 | Week 12 | Week 16 | Week 20 | Week 24 | Week 28 | Week 32 | Week 36 | Week 40 | Week 44 | Week 48 | Week 52 | Early Discontinuation | Week 56 | Week 60 | Week 64 | Week 68 | Week 72 | Week 76/ Follow-up D/C |
| Local urine pregnancy test | × | × | × | × | × | × | × | × | × | × | × | × | × | × | × | × | × | × | × | × | × | ✓ |
| Pharmacokinetic (PK) and ADA sample collections | | ✓ | | | ✓ | | | ~ | | | ✓ | | | | ✓ | × | | | | | | |
| Biomarker Samples whole blood (DNA/RNA/Serum/Plasma) | | × | | | × | | | ~ | | | < | | | | × | × | | | | | | |
| IMAGING | | | | | | | | | | | | | | • | | | | | | | | |
| Brain and cervical spinal cord MRI | Image: A second s | | | | | | | × | | | | | | | × | × | | | | | | |
| R TREATMENT | | | | | | | | | | | | | | | | | | | | | | |
| Randomization/Drug assignment | | × | | | | | | | | | | | | | | | | | | | | |
| Pharmacy Prepares Study Drug or Placebo for Infusion | | × | 1 | ~ | ~ | ~ | ~ | ~ | × | ~ | ~ | × | 1 | ~ | | | | | | | | |
| Administer Infusion & Observation | | ✓ | × | × | × | × | × | × | × | × | × | × | × | × | | | | | | | | |
| ACTIGRAPHY | | | _ | | | | | - | | | | | _ | | | | | | | | | |
| Wearable device training | | × | | | | | | | | | | | | | | | | | | | | |
| Reminder telephone call to subject after Week 0 - Baseline to bring in actigraphy equipment to visit. Equipment will be worn during visits and for 7 days afterwards. | | * | | | | | | ~ | | | * | | | | ~ | | | | * | | | |
| Actigraphy data collected | | × | | | | | | × | | | × | | | | × | | | | | | | |

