- Disability progression response rate on the Expanded Disability Status Scale Plus (EDSS +) (T25FW, 9-Hole Peg test [9HPT, either hand], EDSS) and for each EDSS + component
- 12- and 24-week confirmed disability improvement response rate on the EDSS + and for each EDSS + component
- Change from Baseline on the Multiple Sclerosis Impact Scale (MSIS-29) total score at Weeks 12, 24, 36, and 52
- Change from Baseline on the Modified Fatigue Impact Scale (MFIS) total score at Weeks 12, 24, 36, and 52
- Change from Baseline on cognition battery at Weeks 12, 24, 36, and 52:
 - Total score of the Symbol Digit Modalities Test (SDMT) Oral Version
 - Total score and T-score of the Brief Assessment of Cognition Verbal Memory - Immediate Recall – BAC App Version
 - Total score and T-score of the Brief Assessment of Cognition Tower of London – BAC App Version
- Change from Baseline on the Low Contrast Visual Acuity (LCVA) assessments at Weeks 12, 24, 36, and 52
- Change from Baseline in select plasma biomarkers for monitoring target binding, neuroprotection and/or neurorestoration at Weeks 12, 24, 36, and 52
- Change from Baseline on the MS Individualized Outcome Assessment (MSIOA) overall symptom score and most bothersome symptom score scale at Weeks 24, and 52
- Change from Week 0 in average daily step count and other activity measures (as described in Section 9.4.3) via home actigraphy with wearable biosensor initiated at Weeks 24, 36, and 52
- Summary of variables from brain MRI at Baseline, Weeks 24 and 52
 - Presence of active lesions T1 Gadolinium (GAD)-enhancing lesions
 - Presence of active new and enlarging T2 hyperintense lesions
 - Cumulative number of total T1 GAD-enhancing lesions
 - Cumulative number of total T2 hyperintense lesions
 - Cumulative number of post-baseline T1 GAD-enhancing lesions

- Cumulative number of post-baseline new and enlarging T2 lesions
- Number of T1 GAD-enhancing lesions at each visit
- Change from Baseline in total volumes of (T1 GAD-enhancing lesions)
- Change from Baseline in total volume of T2 hyperintense lesions
- Change from Baseline in whole brain, gray matter (GM), thalamus, white matter (WM) and normal appearing white matter (NAWM) volumes
- Change from Baseline in regional magnetization transfer ratio (MTR) parameters for whole brain, and NAWM, and MTR for T2 lesions
- Change from baseline in lesion MTR for T1 (GAD)-enhancing lesions and delta MTR

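### The SAP's actigraphy rules let worn days without walking and very short wear days distort the averages, and leave the named endpoint, average daily step count, without an analysis

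*SAP*

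**What the plan says.** **The endpoint.** Protocol 3.7 (exploratory endpoint 11) lists "Change from Baseline in one week average daily step count and other activity measures". SAP 4.3.3 lists "Change from Week 0 in average daily step count and other activity measures (as described in Section 9.4.3". SAP 9.4.3 is the T25FW section; actigraphy is in SAP 9.4.9.

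**Steps and durations.** Under SAP 9.4.9, moving duration, walking duration, steps and resting duration are "normalized for the number of hours per day the subject is wearing the device". The visit value is then "the sum of the daily average hourly values for that parameter divided by the number of days" the sensor was worn. The change from Week 0 is analysed on this hourly value.

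**Cadence.** Gait cadence is not normalized for wear. Its visit value is "the sum of the daily mean gait cadence values divided by the number of days the subject wore a sensor".

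**Wear period.** Protocol 4.1 states: "Subjects will be required to use the wearable device for 7 consecutive days at four time points". It has wear start at the Week 0 visit, but after the visits at Weeks 24, 36 and 52. Protocol Appendix D says: "Equipment will be worn during visits and for 7 days afterwards". SAP 9.4.9 describes 7 days starting at the visits, and counts days within a window that it does not define.

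The supplied text gives no minimum wear hours, no minimum number of days, and no rule for a worn day without a cadence value.

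**The concern.** Actigraphy is the trial's only device-based measure of walking outside the clinic. Eligible subjects may have an EDSS up to 6.5, so days with little or no recorded walking are plausible.

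1. **Cadence.** The numerator can draw only on days with walking, while the divisor counts every worn day. The result then mixes how fast a subject walks with how many days the subject walked.
2. **Weighting.** A day with one hour of wear counts as much as a full day, so a rate from a small and perhaps unrepresentative slice of time can move the weekly value.
3. **Endpoint.** Both documents name a daily step count, but the analysis section never produces one. The SAP's own pointer to the details leads to another endpoint.

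SAP 9.4.9 asks for a pooled standard deviation and an effect size with a confidence interval. Noise from wear habits would enlarge the standard deviation and shrink the effect size. A result could also be reported as the step-count endpoint when it is a different quantity.

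**Working it through.** The plan gives no figure to reproduce here. The rules of SAP 9.4.9 were applied as written and compared with the alternatives. The 7-day period comes from the documents. **Steps, wear hours and cadence are assumptions**, because the documents give no wear or activity data.

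**1. Cadence.** SAP rule: sum of daily mean cadence ÷ days worn. Alternative: the same sum ÷ days with a cadence value.

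- 90 steps/min on 5 of 7 worn days: SAP 5 × 90 / 7 = 64.3; alternative 90. The difference is −29%.
- Cadence constant at 100, with a value on k of 7 worn days:

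| k | SAP value | Difference from 100 |
|---|---|---|
| 7 | 100.0 | 0% |
| 6 | 85.7 | −14.3% |
| 5 | 71.4 | −28.6% |
| 4 | 57.1 | −42.9% |
| 3 | 42.9 | −57.1% |

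- Cadence 100 on all 7 days at Week 0, later 105 on 5 of 7 days: SAP 5 × 105 / 7 = 75.0, a fall of 25% although cadence on walking days rose 5%.

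The first row of the table shows that the fault disappears when every worn day has a value.

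**2. Weighting.** SAP rule: mean over days of (steps ÷ hours). Alternative: total steps ÷ total hours.

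- Six 14-h days at 250 steps/h and one 1-h day with 1,200 steps. SAP: (6 × 250 + 1,200) / 7 = 386 steps/h. Pooled: (6 × 14 × 250 + 1,200) / (84 + 1) = 22,200 / 85 = 261 steps/h. The short day is 1/85 = 1.2% of the wear time and has 1/7 = 14.3% of the weight. Its rate is 4.8 times that of the other days, so this is a strong case.
- Range: seven 16-h days of 4,000 steps give 250 steps/h. Replace one of them by a 1-h day:

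| Steps in the 1-h day | SAP (steps/h) | Change | Pooled (steps/h) | Change |
|---|---|---|---|---|
| 0 | 214.3 | −14.3% | 247.4 | −1.0% |
| 600 | 300.0 | +20.0% | 253.6 | +1.4% |
| 1,000 | 357.1 | +42.9% | 257.7 | +3.1% |
| 1,500 | 428.6 | +71.4% | 262.9 | +5.2% |

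**3. Daily count against hourly rate.** The two quantities are not interchangeable.

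- 4,000 steps every day, wear rising from 16 to 24 h: the hourly rate goes from 250.0 to 166.7 (−33.3%); the daily count is unchanged.
- The reverse weakness: in the table's row with 600 steps, the mean daily count is (6 × 4,000 + 600) / 7 = 3,514, a fall of 12.1% from 4,000 caused only by lost wear on one day. The pooled hourly rate moves by 1.4%.

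Each measure reacts to wear in its own way, so both are needed, together with the wear time itself.

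**The case against.** **Wear-time normalization is defensible.** This stands, as the last example shows. A reader might infer that the hourly rate points the wrong way. Suppose 4,500 steps in 15 h become 3,200 steps in 8 h: the rate rises 33% (300 to 400 steps/h) while the recorded count falls 29%. But 7 hours of wear have been lost, and (4,500 − 3,200) / 7 = 186 steps/h in those hours, below both observed rates, would erase the fall. Such a case does not show which figure misleads. The documents do not support ranking the daily count above the hourly rate; they show only that the named measure is missing.

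**The clinic day.** A reader might also infer that the infusion visit day is always in the window and biases the result, since Weeks 0, 24 and 36 are infusion visits and Week 52 is not. The documents disagree on whether the later visit days count. All arms also have the same infusion visits and infusion times, so this asymmetry does not by itself bias elezanumab against placebo. Only the need to reconcile the texts stands.

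**Wear rules may exist elsewhere.** The Operations Manual and the statistical programming plan were not supplied and may set a minimum wear time or define the window. The absence can be stated only for the supplied text.

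**The sizes rest on invented weeks.** This is true. How often days are worn without walking, or for only an hour, is unknown. Nothing in the documents indicates that wear differs by arm in this double-blind trial.

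**Conclusion.** The point holds for an exploratory endpoint. As written, the cadence rule understates cadence whenever a worn day has no recorded walking, and the equal-weight rule lets a very short day dominate. Average daily step count, named in Protocol 3.7 and SAP 4.3.3, has no analysis in SAP 9.4.9, and the cross-reference to it is wrong. This last fault needs no assumption about wear.

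The sizes are illustrations: 64.3 instead of 90 for cadence, and 386 instead of 261 steps/h for weighting. The cadence fault is nil if every worn day has a value, and the weighting fault is small if wear is similar from day to day.

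The primary and secondary results are unaffected. A reader might infer a biased treatment comparison. That would need wear, or the number of non-walking days, to differ by arm, and the documents give no evidence of it. Otherwise the effect is added noise.

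**What to change.** In SAP 9.4.9:

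- Divide summed cadence by the number of days with a recorded cadence, and state that a worn day without detected walking has no cadence value rather than zero.
- Compute the hourly measures as the total over the week divided by total wear hours.
- Add the named average daily step count, on days meeting a pre-set minimum wear time, alongside the hourly rate. The documents offer no basis for a particular cut-off, so the sponsor should choose and justify one.
- Tabulate wear time by arm and visit, together with the number of worn days without recorded walking.

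In SAP 4.3.3, change the reference from Section 9.4.3 to 9.4.9. Reconcile Protocol 4.1, Protocol Appendix D and SAP 9.4.9 on whether the visit day belongs to the 7-day window, and define that window.

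The cost is wording and programming; the SAP's normalization already uses device wear time. The downside is that some subject-weeks with little wear or no recorded walking drop out, which the tabulation makes visible. Protocol Appendix E reports that an efficacy analysis has already been done, so revised results should be labelled as such and shown beside those from the rule as written.

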9.4.10 Biomarkers

The change from baseline in the serum/plasma biomarkers repulsive guidance molecule a (RGMa), neurofilament light (NFL), micro RNA miR-146a and miR-338, mRNAs for PLP1 (proteolipid protein 1), glial fibrillary acidic protein (GFAP), and BDNF (brainderived neurotrophic factor), will be summarized using an MMRM. The model will include the fixed effects of treatment, visit, the stratification factors of diagnosis of MS (PPMS or nrSPMS) and background MS immunotherapy (Yes or No), and the treatmentby-visit interaction, with baseline value for the respective parameter as a covariate. The REPEATED statement will be used for visit with blocks in the covariance matrix identified by subject nested within treatment group. The unstructured covariance structure will be used to estimate the within subject variance-covariance.

9.4.11 MRI Parameters

The MRI parameters of interest and analyses are listed in Section 4.3.3.

The number and percentage of subjects with active lesions will be summarized for T1 GAD-enhancing lesions and T2 hyperintense lesions (separately). The difference in the proportion between elezanumab and placebo groups with the 95% confidence interval for the difference based on Wald confidence limits will be presented.

The cumulative number of total T1 GAD-enhancing lesions, cumulative number of total T2 hyperintense lesions, cumulative number of post-baseline T1 GAD-enhancing lesions, cumulative number of post-baseline new and enlarging T2-lesions, will be summarized with continuously and analyzed using an analysis of covariance (ANCOVA). The model for the analysis of the cumulative number of total lesions will include treatment, the stratification factors of diagnosis of MS (PPMS or nrSPMS) and background MS immunotherapy (Yes or No). For the cumulative number of lesions during the treatment period, only subjects with Baseline, Week 24, and Week 52 MRIs will be included. For the cumulative number of lesions post-baseline, only subjects with Week 24 and Week 52 will be included.

The number of T1 GAD-enhancing lesions at each visit (Baseline, Week 24, Week 52) will be summarized categorically with the number and percent of subjects for the following categories: 0, 1, 2, 3, 4, 5, > 5.

The following endpoints will be analyzed using change or percent change from baseline using an ANCOVA model.

- Change from Baseline in total volumes of T1 GAD-enhancing lesions •
- Change from Baseline in total volume of T2 hyperintense lesions
- Percent change from Baseline in whole brain, gray matter (GM), thalamus, white matter (WM) and normal appearing white matter (NAWM) volumes
- Change from Baseline in regional magnetization transfer ratio (MTR) parameters for whole brain, and NAWM, and MTR for T2 lesions
- Change from Baseline in diffusion tensor imaging (DTI) parameters (fractional anisotropy and Apparent Diffusion Coefficient (ADC)) for whole brain, NAWM and T2 hyperintense lesions
- Change from Baseline in cervical spinal cord area, volume and number of lesions
- Change from Baseline in regional MTR for cervical spinal cord lesions
- Change from baseline in DTI parameters (fractional anisotropy and ADC) for cervical spinal cord

The model for the change from baseline analysis will include treatment, the stratification factors of diagnosis of MS (PPMS or nrSPMS) and background MS immunotherapy (Yes or No), and the baseline value. For each treatment group, the number of subjects, mean, standard deviation, minimum, and maximum, will be presented, as well as the LS means and standard error, and the between group difference, standard error, and 95% confidence interval.

The change from baseline in lesion MTR for T1 GAD-enhancing lesions and delta MTR will be analyzed using an MMRM. The change from baseline will be calculated for each unique lesion within a treatment group. A dummy code will be created based on each

subject-lesion to describe each unique lesion. The model will include the fixed effects of treatment, visit, the stratification factors of diagnosis of MS (PPMS or nrSPMS) and background MS immunotherapy (Yes or No), and the treatment-by-visit interaction, with baseline MTR value as a covariate. The RANDOM statement will be used for each subject. The REPEATED statement will be used for visit with blocks in the covariance matrix identified by unique lesion nested within subject nested within treatment group. The unstructured covariance structure will be used to estimate the within subject variancecovariance. If the model fails to converge, the first order autoregressive (AR[1]) covariance structure will be substituted. If the model still fails to converge, the compound symmetry (CS) covariance structure will be substituted. Denominator degrees of freedom will be computed using the Kenward-Roger method.

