9.0 Efficacy Analyses

9.1 General Considerations

All efficacy endpoints will be analyzed on mITT analysis set. The primary and secondary efficacy endpoints analyses will be repeated for the on the RF analysis set and the MMIA set as described in Section 5.1. Additional exploratory analyses will be repeated based on a subset of the population with a pre-defined deficit at baseline where noted.

For all exploratory efficacy analyses other than those related to MRI variables, where a continuous summary by visit is noted, the descriptive statistics will be provided by treatment group. The statistics include number of observations, mean, standard deviation, minimum, median, and maximum. The number and percentage will be summarized for categorical variables.

For all efficacy endpoints where change from baseline will be analyzed with an MMRM, the mean at baseline and that visit will be presented, as well as the LS means standard error, and the between group difference, standard error, and 95% confidence interval.

Baseline for efficacy will be defined as the last non-missing observation that is on or before the first dose date.

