11.0 Summary of Changes

11.1 Summary of Changes Between the Previous Version and the Current Version

Minor typographical corrections and text clarifications were made throughout.

An interim futility analysis previously planned was eliminated. Sample size calculations have been corrected.

Due to an update to the format corresponding document to further define programming, the statistical programming plan, the following sections were added:

- Subject Disposition
- Extent of Exposure and Compliance
- Demographics, Baseline Characteristics, Medical History and Prior/Concomitant Medications
- Protocol Deviations and Visit Modifications

Due to the COVID-19 pandemic, significant modifications were made to the secondary and exploratory endpoints in the protocol. These changes are reflected in the SAP. Additionally, due to increased missing data, an additional analysis set (MMIA set) was added, and missing data handling rules were updated.

Details of the analyses of exploratory endpoints and MRI were added.

Additional efficacy analyses were added to further characterize the treatment effect, including:

- Improvement by visit on the EDSS + and its components
- Disability progression
- Continuous analyses of the change from baseline in T25FW and 9HPT
- Analyses of the SDMT, MFIS-5, and LCVA based on a subset of the population with a deficit at baseline

- Exploratory analyses related to biomarkers and actigraphy
- Figures specified in Section 9.6

Minor clarifications and updates were made to the safety analyses. The adverse events of special interest were updated in the protocol and is reflected in this SAP. A change from baseline summary is planned for specified laboratory values only. A summary of liver function tests including possible Hy's Law cases is specified. The PCS laboratory table was updated to reflect only the parameters which were collected in this study. A summary of the number MS relapses is planned. Details of the vital signs summaries were added.

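### The ANCOVA for the two exploratory cumulative total lesion counts omits the baseline lesion count; precision may be lost, by an amount the documents do not fix

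*SAP*

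**What the plan says.** SAP 4.3.3 lists the cumulative totals, including "Cumulative number of total T2 hyperintense lesions", among the exploratory endpoints. It lists the cumulative post-baseline counts (T1 GAD-enhancing, and new and enlarging T2) as separate items.

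SAP 9.4.11 assigns all four counts to ANCOVA. Its one model sentence for them reads "The model for the analysis of the cumulative number of total lesions will include treatment, the stratification factors" (MS diagnosis and background immunotherapy). No baseline lesion count appears there or elsewhere in the SAP, and no reason is given.

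On scans, the same section says: "For the cumulative number of lesions during the treatment period, only subjects with Baseline, Week 24, and Week 52 MRIs will be included". For the post-baseline counts it asks only for Week 24 and Week 52.

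Other models in the SAP do carry a baseline term:

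- The change-from-baseline MRI ANCOVA in 9.4.11 ends with "background MS immunotherapy (Yes or No), and the baseline value". Its endpoints include the number of cervical cord lesions.
- The biomarker model in 9.4.10 is fitted "with baseline value for the respective parameter as a covariate".
- The primary ORS model in 9.2 adjusts for the baseline scores of all four components.

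SAP 9.1 states: "Baseline for efficacy will be defined as the last non-missing observation that is on or before the first dose date". Protocol Appendix D schedules MRI at Screening, Week 24 and Week 52 (and at early discontinuation), so the Baseline scan is the Screening scan, taken before treatment.

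**The concern.** As listed, the model has only categorical terms: it is called an analysis of covariance but has no covariate. A baseline lesion count is likely to predict later counts. If the Baseline scan is itself added into the total, part of the outcome is a quantity that treatment cannot affect. Leaving it unadjusted puts that variation into the residual and lets any chance imbalance between arms at baseline pass straight into the estimated difference.

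What is at stake is the width of the intervals for two exploratory comparisons with about 30 subjects per arm.

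**Working it through.** **Inputs.** The plan gives no power or precision figure for lesion counts. Its trial-level figure in SAP 4.4 (effect size 0.59, one-sided 0.1, about 30 per arm, about 10% dropout, about 80% power) does reproduce. With 30 × 0.9 = 27 per arm, 0.59 × √(27/2) = 2.168; less 1.282 this is 0.886, so power is 0.812 (0.808 with the noncentral t). This supports 27 per arm as a working number and says nothing about lesions. The between-scan correlation r and the lesion-count variances are not in the documents; r from 0 to 0.9 is assumed.

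**Step 1: total as a sum over scans.** Let B, W24 and W52 be the counts at the three scans, with equal variance (set to 1) and common correlation r. Strata are taken to explain nothing.

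- Baseline summed, unadjusted: Var(B + W24 + W52) = 3 + 6r
- Baseline not summed, unadjusted: Var(W24 + W52) = 2 + 2r
- Either one, given B: 2 + 2r − 4r²

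| r | 3 + 6r | 2 + 2r | 2 + 2r − 4r² | Factor, baseline summed | Factor, not summed |
|---|---|---|---|---|---|
| 0 | 3.0 | 2.0 | 2.00 | 1.5 | 1.0 |
| 0.5 | 6.0 | 3.0 | 2.00 | 3.0 | 1.5 |
| 0.9 | 8.4 | 3.8 | 0.56 | 15 | 6.8 |

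Each factor is the amount by which adding baseline divides the variance of the treatment difference. On the standard-error scale, the summed column is √1.5 = 1.22, √3 = 1.73 and √15 = 3.87.

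**Step 2: dependence on equal variances.** If the baseline variance is k times the later-scan variance, the summed numerator becomes k + 2 + 4r√k + 2r and the denominator is unchanged. At k = 0.25 the factors are 2.25/2 = 1.1, 4.25/2 = 2.1 and 5.85/0.56 = 10.4. So 1.5 is not a floor.

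**Step 3: check on skewed counts.** Gamma-Poisson counts were simulated with 27 per arm, two binary strata, mean 0.3 per scan and gamma shape 0.3 (assumed values). The subject-level variance is 0.3²/0.3 = 0.3 and the Poisson variance is 0.3, so r = 0.3/0.6 = 0.5. The adjusted-to-unadjusted standard-error ratio was 0.568, a variance factor of 1/0.568² = 3.1 against 3.0 from the formula.

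**Step 4: comparison with what is already planned.** Write the total as Y = B + P, with P the post-baseline part. Once B is in the model, Y and P differ only by a term the model already contains, so the treatment coefficient for Y given B equals that for P given B in the same subjects.

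- T1 GAD: P is the post-baseline count already planned. If that count is analysed without baseline, the extra gain is the not-summed column; if with baseline, it is nil.
- T2 as baseline plus new lesions N: with m = Var(N)/Var(B) and B, N uncorrelated, adjustment divides the variance by 1 + 1/m, that is 11, 2.0 or 1.25 for m = 0.1, 1 or 4. The adjusted variance is then m, which is the unadjusted variance of N. Against a count of N the extra gain is m/m = 1.0, and the planned new-and-enlarging T2 count is close to N, though not identical.
- T2 as a sum over scans: P is then the sum of all T2 lesions at Weeks 24 and 52, which no planned endpoint supplies.

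**Step 5: cost in degrees of freedom.** 81 subjects less 5 parameters (intercept, two treatment, two strata) leaves 76. With the covariate it is 75.

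**The case against.** The strongest opposing case has four parts.

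1. **The scan rule is not written for the totals.** It is written for lesions during the treatment period, and the model sentence uses the word total. Equating the two, and counting the Baseline scan in the sum, is plausible because the post-baseline rule needs only two scans, but it is an inference. SAP 11.1 mentions a separate statistical programming plan, not available here, that may settle which scans are summed. This stands.
2. **The large factors flatter the fix.** They compare the adjusted total with the unadjusted total, when neighbouring endpoints already deliver much of the gain. T2 volume is also planned, with baseline adjustment. This stands, as step 4 shows.
3. **There is no contradiction in the SAP.** The models that carry a baseline term are for change from baseline (or, for ORS, a score built on it), and each uses its own baseline. A cumulative count may be modelled differently by choice. This stands too, although cervical cord lesion number is a lesion count in the same section and is adjusted.
4. **The timing is late.** Protocol Appendix E reports that a planned efficacy analysis has been done and found no benefit on any endpoint, so a covariate added now follows known results. This affects how the analysis is labelled, not whether the covariate is useful.

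A reader might infer more than the documents support. One inference is that the planned comparison is biased. Randomization protects it, and in simulated null trials (3,000 per setting, 27 per arm) two-sided 0.05 rejection was 3.9% to 5.9% with or without the covariate. Another is that at least a third of the variance is wasted. That needs the baseline scan in the sum and equal variances, and neither is stated.

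**Conclusion.** The omission is real: the stated model for the two cumulative totals has no baseline lesion count, and nothing else in the SAP supplies one. The consequence is a possible loss of precision on two exploratory endpoints. SAP 4.6 applies no multiplicity adjustment, and the primary ORS analysis is unaffected.

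The size cannot be fixed from the documents. The table in the working gives a range that depends wholly on the assumed correlation and on equal variances, and at zero correlation with the baseline scan left out of the sum there is no gain. For T1 GAD, and for T2 if the total means baseline plus new lesions, most of the apparent gain duplicates what the post-baseline counts can already provide. A distinct gain remains mainly if total T2 counts are summed over scans, and it would be larger if lesions persist from scan to scan. This is worth considering, not a serious flaw. Confidence is high in the omission and lower in how much it matters.

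**What to change.** Add the respective baseline lesion count (T1 GAD-enhancing or T2) as a covariate in the ANCOVA for the cumulative totals, as 9.4.11 already does for the change-from-baseline MRI endpoints. If results are already known, as Protocol Appendix E indicates, keep the model as planned and report the adjusted one beside it as a labelled supplementary analysis.

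The cost is a sentence of text and one degree of freedom. No subject is lost if the rule requiring a Baseline scan applies to the totals, as inferred. If it does not, any subject without a Screening scan would drop out of the adjusted model.

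Two clarifications could go in with the same edit, though the point does not depend on them: which scans are summed (for T2, a sum over scans or baseline plus new lesions), and which covariates apply to the two post-baseline counts.
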